**Table 2. Patient Cohort Assignment, Dose and Safety Margins**

Cohort	No. of Infusions	Target Mean Particles per kg	Target Mean TGPU per kg	Estimated Total Vol. Infused based on a 70kg patient and a mean Thrombosomes conc. of $1.61 \times 10^9$ particles per ml with an associated 2800 TGPU per ml 	Safety Margin 	
					Particles infused per kg	TGPU infused per kg
1 (Patients 1-8)	1	$9.45 \times 10^7$	165	4.1 ml	300	301
2 (Patients 9-16)	1	$1.89 \times 10^8$	330	8.2 ml	150	150
3 (Patients 17-24)	1	$3.78 \times 10^8$	660	16.4ml	75	75

Doses will be adjusted per weight of each patient, Estimated Total Volume Infused based on a 70kg patient and a mean Thrombosomes concentration of  $1.7 \times 10^9$  particles per ml with an associated 3400 TGPU. Example Total Dose in ml = (Weight in kg X (desired Dose in particle count or TGPU, specific for each cohort))/ Thrombosomes particle count or TGPU per ml provided with each lot of Thrombosomes. EXAMPLE for Cohort 1:  $70 \times (9.45 \times 10^7) / 1.7 \times 10^9$  per ml = 5.5ml

Safety margin based on the single acute toxicity study in NZWR (MPI 1542-001)

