## 1.7 Product Information & Indications for Use

Thrombosomes are a lyophilized product prepared from a pool of group O human platelets (collected from 5-10 donors) that are being developed for the treatment of uncontrolled hemorrhage. Each vial from each lot of Thrombosomes contains a mean of 1.7 x 10^9 Thrombosomes particles per ml and an associated activity of approximately 3400 TGPU per ml after rehydration with 10 ml of sterile water for injection. Based upon efficacy studies in a thrombocytopenic New Zealand White Rabbit (NZWR) ear bleed model, the lowest observed efficacious dose was (1.89 x 10^8 particles per kg or 330 TGPU per kg). Refer to the *Investigator's Brochure* for additional information.

---

 National Highway Traffic Safety Administration Fatality Analysis Reporting System (FARS) 1975-2009 – <http://nhtsa.gov/FARS>

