### 1.8.1 Primary

- Assess the safety of infusing increasing doses (approximately 5 ml, 10 ml, and 20 ml) of allogeneic Thrombosomes which are equivalent to approximately  $9.45 \times 10^7$  particles/kg or 165 TGPU per kg,  $1.89 \times 10^8$  particles/kg or 330 TGPU per kg and  $3.78 \times 10^8$  particles/kg or 660 TGPU per kg, respectively.

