All enrolled patients with active bleeding of modified WHO Grade 1 (subset of patients with either epistaxis, hematuria, oral petechiae, oropharyngeal bleeding, or bleeding at invasive or other wound sites) or Grade 2 bleeding will receive Thrombosomes. Grades 0, 3, or 4 bleeding are not inclusion criteria for enrollment. Active bleeding is defined as to occur within 4 days of infusion. If the patient progresses to grade 3 or 4 bleeding during that time, they will be excluded from the study and will not be infused. Doses will be adjusted per weight of each patient. The starting dose for patients in Cohort 1 will be approximately 5 ml of Thrombosomes or approximately  $9.45 \times 10^7$  particles/kg or 165 TGPU per kg by IV infusion. The dose for patients in Cohort 2 will be approximately 10 ml of Thrombosomes or approximately  $1.89 \times 10^8$  particles/kg or 330 TGPU per kg by IV infusion. The dose for patients in Cohort 3 will be one dose of approximately 20 ml of Thrombosomes or approximately  $3.78 \times 10^8$  particles/kg or 660 TGPU per kg by IV infusion. See Table 2.

Pre-infusion, infusion (Day 1), and post-infusion follow up through Day 30 (+2 days) will be performed as outlined in *Table 4* below. Patients require observation at a minimum through the completion of Visit 4 (6 hours post-infusion). Patients may be admitted and observed overnight at the discretion of the PI. If the subject is an in-patient on Days 3-5, he/she should be assessed and samples collected as described in Table 4.

All patients in each cohort will be evaluated for any signs of AEs, serious adverse events (SAEs) and serious adverse drug reactions (SADRs) after infusion.

Patient infusions cannot occur on the same day. Once an enrolled patient has been infused, he/she must reach Day 4 without a suspension or stopping rule (1.9.8 Stopping Rules and Procedures for Study) event being reported prior to a subsequent patient being infused. In addition, there will be at least a two-week interval between cohorts to allow an independent Data Monitoring Committee (DMC) to review all patients' accumulated safety data after visit Day 6 from Cohort 1 and then again after the last patient from Cohort 2 has completed visit Day 6 in order to recommend whether the study should advance to the next cohort. Refer to Appendix B- Flow Diagram of Study Events.

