## 2 STUDY OBJECTIVES AND ENDPOINTS

### 2.1 Study Objectives

#### 2.1.1 Primary Objective

The primary objective of this study is to assess the effect of escalating infusion doses of Thrombosomes on the safety of actively-bleeding, thrombocytopenic patients.

Three dose levels, including 5 mL ( $9.45 \times 10^7$  particles/kg or 165 thrombin generation potency units [TGPU] per kg), 10 mL ( $1.89 \times 10^8$  particles/kg or 330 TGPU/kg), and 20 mL ( $3.78 \times 10^8$  particles/kg or 660 TGPU/kg), will be studied across 3 sequentially enrolled patient cohorts. Incidence of treatment-emergent adverse events (TEAEs) and serious adverse events (TESAEs), application of suspension or stopping rules, and abnormality or worsening in measures of bleeding severity, coagulation, hematology, serum chemistry, vital signs, and cardiac, physical, and neurologic statuses will be used as indicators of safety.

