**Table 1 – Patient Cohort Assignment, Target Dose, and Safety Margins**

Cohort	No. of Infusions	Target Mean Particles/kg	Target Mean TGPU/kg	Estimated Total Volume Infused 	Safety Margin 	
					Infused Particles/kg	Infused TGPU/kg
Cohort 1 (patients 1-8)	1	$9.45 \times 10^7$	165	4.1 mL	300	301
Cohort 2 (patients 9-16)	1	$1.89 \times 10^8$	330	8.2 mL	150	150
Cohort 3 (patients 17-24)	1	$3.78 \times 10^8$	660	16.4 mL	75	75

Abbreviation: TGPU, thrombin generation potency units.

 Estimated Total Volume Infused is based on a 70-kg patient and mean Thrombosomes concentration (across lots) of  $1.61 \times 10^9$  particles/mL with associated 2,800 TGPU/mL. Doses will be adjusted by patient weight in order to maintain the target Thrombosomes particle count per kg of patient body weight. Formula: Total Volume Infused in mL = ([patient weight in kg] x [desired dose in particles/kg or TGPU/kg, specific for the cohort]) ÷ Thrombosomes particles/mL or TGPU/mL provided with the specific lot of Thrombosomes. Example for Cohort 1: 4.1 mL = ([70 kg] x [ $9.45 \times 10^7$  particles/kg]) ÷  $1.61 \times 10^9$  particles/mL.

 Safety margins are based on the single acute toxicity study in New Zealand white rabbits (see CSP Section 1.7).

Written informed consent will be obtained from patients who are either actively bleeding or at risk of bleeding within 4 weeks following screening. Patients who are actively bleeding and determined through screening assessments to meet eligibility criteria for study participation will be immediately scheduled for infusion with Thrombosomes to occur within 4 days of screening. Patients who are not actively bleeding during screening but are at risk for bleeding within 4 weeks, based on medical history and projected clinical course, will be monitored for bleeding. If bleeding begins within 4 days (+6 hours), complete rescreening will not be necessary, but updated WHO bleeding assessment and complete blood count (CBC) tests will be required for determination of eligibility. If bleeding begins >4 days later but within 4 weeks of initiation of screening, rescreening (inclusive of all original screening assessments) will be necessary for

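### Protocol Table 2 footnote 1 misworks its own Cohort 1 dose example (5.5 ml printed, 3.89 ml from its inputs) on a concentration that contradicts the column it annotates; SAP 8.6 then reports the target as the dose given

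*Protocol*

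**What the plan says.** Protocol Table 2 sets three target doses: 9.45 × 10⁷, 1.89 × 10⁸ and 3.78 × 10⁸ particles/kg, paired with 165, 330 and 660 TGPU/kg. It lists estimated infused volumes of 4.1, 8.2 and 16.4 ml. The column header ties these volumes to a 70-kg patient and "a mean Thrombosomes conc. of $1.61 \times 10^9$ particles per ml with an associated 2800 TGPU per ml".

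Footnote 1, attached to that header, says the same volumes rest on 1.7 × 10⁹ particles/ml and 3400 TGPU. It gives a formula (weight × target ÷ lot concentration) in which the target is the "desired Dose in particle count or TGPU, specific for each cohort", and it closes with "70 \times (9.45 \times 10^7) / 1.7 \times 10^9$ per ml = 5.5ml".

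Other places bear on this:

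- Protocol 1.7 agrees with the footnote's concentration: a mean of 1.7 × 10⁹ "Thrombosomes particles per ml and an associated activity of approximately 3400 TGPU per ml after rehydration".
- SAP Table 1 carries the same volumes on 1.61 × 10⁹ and 2,800, and its worked example begins "Example for Cohort 1: 4.1 mL = ([70 kg] x".
- Protocol 1.8.1 describes the doses by volume: "Assess the safety of infusing increasing doses (approximately 5 ml, 10 ml, and 20 ml) of allogeneic Thrombosomes". Protocol 1.9.2.1 does likewise: "The starting dose for patients in Cohort 1 will be approximately 5 ml of Thrombosomes". SAP 2.1.1 has "Three dose levels, including 5 mL", without the qualifier.
- Protocol Appendix F.3 says a dose table for each lot is supplied in the EDC, and it works a site-level example from a label dosage in ml/kg.
- SAP 8.6 defines total volume infused as weight × target particles/kg ÷ lot concentration. It then obtains particles infused, and particles/kg, from that volume. The same list includes whether the infusion was interrupted and why.

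**The concern.** Table 2 defines the dose levels of a dose-escalation safety study. A reader should be able to take its stated basis, apply its formula and recover its volumes. Here the only worked example in the table does not follow from its own inputs, and the footnote names a different product concentration from the header it explains. The protocol and SAP therefore print different answers, 5.5 and 4.1 ml, for the same 70-kg Cohort 1 patient.

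The SAP 8.6 point matters for a related reason. The exposure table is where one would check that patients received what Table 2 intended. If the volume is back-calculated from the target, the table cannot show a departure from the target.

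**Working it through.** **Inputs.** Weight 70 kg. Cohort targets and both concentration pairs as in Protocol Table 2. Formula from footnote 1: volume = weight × dose per kg ÷ concentration per ml.

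**Table body, header basis (1.61 × 10⁹ particles/ml).**

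- Cohort 1: 70 × 9.45 × 10⁷ ÷ 1.61 × 10⁹ = 4.11 ml (printed 4.1)
- Cohort 2: 70 × 1.89 × 10⁸ ÷ 1.61 × 10⁹ = 8.22 ml (printed 8.2)
- Cohort 3: 70 × 3.78 × 10⁸ ÷ 1.61 × 10⁹ = 16.43 ml (printed 16.4)

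All three reproduce.

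**Table body, footnote basis (1.7 × 10⁹ particles/ml).** The same steps give 3.89, 7.78 and 15.56 ml. None matches the column.

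**The footnote's example.** 70 × 9.45 × 10⁷ = 6.615 × 10⁹, and 6.615 × 10⁹ ÷ 1.7 × 10⁹ = 3.89 ml. The printed figure is 5.5 ml, and 5.5 ÷ 3.891 = 1.41, so it is 41% too high. Against the header's 4.11 ml it is 34% too high (5.5 ÷ 4.109 = 1.34).

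Other readings do not recover it:

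| Basis | Cohort 1 volume |
|---|---|
| Particles, 1.7 × 10⁹/ml | 3.89 ml |
| TGPU, 70 × 165 ÷ 3400 | 3.40 ml |
| Particles, 1.61 × 10⁹/ml | 4.11 ml |
| TGPU, 70 × 165 ÷ 2800 | 4.13 ml |

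To obtain 5.5 ml at 70 kg, the concentration would have to be 6.615 × 10⁹ ÷ 5.5 = 1.20 × 10⁹ particles/ml, which appears nowhere in the documents.

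**SAP 8.6.** Write W for weight, D for target particles/kg and C for lot concentration. Volume V = W × D ÷ C. Particles infused = C × V = W × D. Particles/kg = W × D ÷ W = D. The result is the target, whatever was given. As a hypothetical case, a Cohort 1 infusion stopped halfway would deliver 9.45 × 10⁷ ÷ 2 = 4.73 × 10⁷ particles/kg and still be tabulated as 9.45 × 10⁷.

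**Two side checks, for clarity only.**

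- Nominal volumes: 5 ÷ 4.109 = 10 ÷ 8.217 = 20 ÷ 16.435 = 1.22, so they lie about 22% above the 70-kg table volumes. On 1.7 × 10⁹ the ratio is 5 ÷ 3.8912 = 1.285, about 28% above.
- Unit: on 1.7 × 10⁹ and 3400, particle-based and TGPU-based volumes differ by 3.891 ÷ 3.397 = 1.145, or 14.5%. On 1.61 × 10⁹ and 2800 they differ by 4.125 ÷ 4.109 = 1.004, or 0.4%.

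**The case against.** The best defence is that the example is illustrative and nobody doses from it. The formula takes each lot's own concentration, a dose table accompanies each lot, the Appendix F.3 example is arithmetically right (70 × 0.1 = 7.0 ml), and SAP Table 1 already shows 4.1 mL. All of this stands, and it is why the point is minor. It does not make the footnote correct.

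Four stronger readings might tempt a reader, and the documents do not support them.

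- **That Cohort 1 patients would be overdosed.** No procedure leads a site to give 5.5 ml, so a dose or safety margin calculated from that volume describes an infusion the plan does not produce.
- **That the documents give four competing volumes for one 70-kg target.** Only 4.1 and 5.5 ml are printed for 70 kg. The 3.89 ml is the correct answer to the footnote's sum and is not printed. The 5, 10 and 20 ml figures are not tied to 70 kg, and the doses are adjusted for weight. At 1.61 × 10⁹, 5 ml meets the Cohort 1 target for a patient of 5 × 1.61 × 10⁹ ÷ 9.45 × 10⁷ = 85 kg.
- **That section 1.7 is wrong, or must carry the same mean as Table 2.** Matching the printed volumes shows which concentration produced the column, not which describes the supplied lots. The two means may refer to different sets of lots.
- **That particles/kg must govern the volume.** SAP Table 1 says weight adjustment maintains the particle count per kg, but its formula still allows either unit. The choice is the sponsor's, and section 1.7 gives its potency figure only as approximate.

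It can also be said that SAP 8.6 is a separate matter from the footnote. That is fair. The error did not arise from the footnote, but it affects the same quantity, the dose per kg, and is cheap to correct at the same time.

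**Conclusion.** Two errors are established. Footnote 1 is arithmetically wrong by 41% on its own inputs, and its concentration basis conflicts with the header and with SAP Table 1. SAP 8.6 defines a delivered dose that equals the target by construction.

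Both are minor. No target dose, endpoint or hypothesis test depends on either, and a misdose is unlikely given the lot-specific tables. The first conclusion rests only on figures printed in Table 2. The second rests on taking the SAP 8.6 formulas as written; whether the actual infused volume is recorded cannot be seen from the protocol or SAP.

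The nominal 5, 10 and 20 ml and the choice of unit are matters of clarity, not errors.

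**What to change.** 1. **Protocol Table 2, footnote 1.** Restate it on the header's basis: 1.61 × 10⁹ particles/ml, 2800 TGPU/ml, example result 4.1 ml. If the sponsor confirms that 1.7 × 10⁹ and 3400 are the right means for this table, give the example as 3.9 ml, change the header, and change the volumes in Table 2 and SAP Table 1 to 3.9, 7.8 and 15.6 ml, with SAP Table 1's stated basis and example to match.
2. **SAP 8.6.** Replace the volume formula with the volume actually infused, and compute particles infused and particles/kg from it. If that volume is not in the infusion data, label the three quantities as planned dose and report interrupted infusions separately.

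Optional: say what weight the nominal 5, 10 and 20 ml assume, and name the unit that sets the volume.

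The cost is one footnote and one SAP definition, with no added patients, visits or tests. The SAP change needs a recorded-volume field. A corrected dose example goes beyond the kinds of administrative change listed in Protocol 1.22.4, so it should be assumed to need IRB and FDA submission. It can wait for the next amendment.

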### 1.9.2.2 Additional Hemostatic Therapy: All Cohorts

This product is not expected to increase the platelet corrected count increment (CCI). The infusion of platelets for six hours prior and one hour after infusion of Thrombosomes is

restricted. However, at any time, if the patient's clinical bleeding remains unchanged or deteriorates with additional or worsening bleeding, the patient's physician(s) may transfuse the patient with blood products, hemostatic agents, or coagulation factors without limitation. The study patient will be followed for safety data for 30 (+2) days post-infusion of the dose of Thrombosomes.

### ***1.9.3 Assessment of Bleeding: Using WHO Bleeding Score***

Use of the WHO (World Health Organization) Bleeding Assessment will provide a standardized approach, across multiple clinical sites, in order to determine study eligibility, for assessing a patient's bleeding during the clinical trial, and for assessing the effect of Thrombosomes (if any) on bleeding. Study personnel conducting the assessment will be trained on the assessment and will be authorized by the PI to perform the assessment. This authorization will be documented on the Authorities and Responsibilities Log. The location of bleeding for all bleeding sites will be assessed by WHO grade during study at screening, (re-screening, if applicable) baseline, 1 hour, 6 hours, 24 hours post-infusion and 6 days post-infusion. In some instances, a bleeding site may not be able to be reassessed post-infusion due to the need for an invasive procedure or other procedure that would add additional risk for the subject. The protocol does not require subjects to undergo medically unnecessary procedures (or risks) only in order to perform post-infusion WHO bleeding assessments. Subjects who are transfused with red cells to treat anemia due to their underlying disease (and not because of bleeding) will not be assessed as having WHO grade 3 bleeding. Anemia from underlying disease will be designated if there is evidence of bone marrow suppression indicated by at least two of the following: leukopenia, thrombocytopenia, or reticulocytopenia; and absence of WHO grade 2 bleeding in the prior 24 hours. For designation of WHO grade 3 bleeding, red cell transfusion must be specifically related to treatment of bleeding within 24 hours of onset of bleeding. (see Table 4. Schedule of Events for timing of WHO bleeding assessments). The same person must perform assessment of pre-infusion and 1-hour post-infusion time points.

To assess bleeding and determine the WHO Bleeding Score, the patient will be interviewed, a physical examination will be performed, and the patient's chart will be reviewed. The WHO Bleeding Score will be determined using Appendix A- Modified WHO Bleeding Score.

### ***1.9.4 Blinding***

This is an open-label safety study.

### ***1.9.5 Duration of Patient Participation and Study***

The duration of the patient's participation on the study is expected to be approximately 4-8 weeks. The time from first patient first visit to last patient last visit is expected to be 18 months.

### ***1.9.6 Patient Compensation***

Patients may or may not be compensated for participation in study. If compensated, the total should not exceed \$1000.00, for time, parking and transportation costs during visits. See Table 3.

**Table 3. Proposed Patient Compensation**

Visit No.	Type of Contact	Cohorts 1, 2 and 3
1	Screening	\$200
2	Infusion Visit	\$200
9	Day 6	\$400
10	Follow-up 30-day visit	\$200
	Total	\$1000

### **1.9.7 Cohort Study Schedule**

The assignment of treatment dose will be determined in sequential order, as shown in Table 2. Patients in Cohorts 2 through 3 will not receive infusion of study material until all eight patients in the previous cohort have received infusion of study treatments and have been observed through the completion of follow up visit Day 6, and the study data has been reviewed by one of the study investigators, the medical monitor, and the DMC. The DMC will meet before initiation of the study in order to approve a charter that will determine the process and schedule for reviewing the safety data, determination of serious adverse events, and the appropriate stopping rules for the study.

### **1.9.8 Stopping Rules and Procedures for Study**

#### **Suspension Rules**

If an SAE is reported to the Sponsor that:

1. the investigator believes is possibly, probably, or definitely related to the use of the product (As defined in 1.22.6.1 Definition of Terms), and
2. does not meet the stopping rules criteria for SAEs listed below, then the Sponsor will confirm relatedness and suspend enrollment and infusion of patients in the study until further evaluation of the SAE is completed. The independent DMC will meet ad hoc to review the results of the event(s) with the Medical Monitor and PI who treated the patient. The DMC will then determine causality and recommend whether the study should either proceed without changes, proceed with modifications, or not proceed. See 1.22.6.4 Adverse Event Reporting for reporting of serious adverse events. Safety reports will be provided to FDA in accordance with 21 CFR 312.32.

#### **Stopping Rules**

The Sponsor will stop enrollment into the study if an SAE of death, thrombotic or embolic event, acute lung injury or anaphylaxis occurs that is directly (probably or definite) related to the product within 48 hours of infusion of Thrombosomes (except for anaphylaxis within 4 hours). If the study is stopped, the study will be restarted only after a complete review of the data is completed by the medical monitor, all PIs and the independent DMC, and it is determined that there is reasonable doubt that the event is related to the product. Safety reports will be provided to FDA in accordance with 21 CFR 312.32.

The following definitions will be used to characterize specific stopping rule SAEs:

- Thrombotic or embolic event (including myocardial infarction, pulmonary embolism, and venous thromboembolism [defined in Appendix C- Definition of Myocardial Infarction and Appendix E- DVT and PE Algorithm Pages from ICSI Guideline, respectively], or stroke [including transient ischemic attack]). A minor catheter thrombosis is not included in this category, or
- Pulmonary adverse event of acute lung injury (ALI) (defined in Appendix D- Definition of ALI), or
- Anaphylaxis (defined in Appendix G – Modified Definition of Anaphylaxis)

An SAE will be considered potentially attributable to the product if there is a high degree of certainty that 1) a relationship to a Thrombosomes infusion exists, 2) there is a reasonable temporal association, and 3) the event cannot be explained by known characteristics of the patient's clinical state or factors including other therapy. For an SAE to be considered to be definitely related to a Thrombosomes infusion, an association exists between the receipt of an investigational product and the event, and an association to other factors has been ruled out (See 1.22.6.2 Relationship to Investigational Product for definitions to determine causality).

### **1.9.9 Safety Endpoints**

Primary: The occurrence and frequency of AEs, SAEs, and thromboembolic events as determined by clinical signs and symptoms, physical exam including neurological assessment, and laboratory studies.

Secondary:

- Describe the effect of increasing doses of allogeneic Thrombosomes on bleeding including changes in WHO bleeding grade.
- Describe the effect of increasing doses of allogeneic Thrombosomes on coagulation measures.

## **1.10 Study Population**

### **1.10.1 Patient Numbers**

Approximate number of patients screened: 120

Approximate number of patients consented: 60

Approximate number of patients enrolled: 30

Maximum Number of Patients Completed: 24 (8 patients in Cohorts 1-3)

Evaluable patients: 24

A patient is evaluable if they have completed their Day 6 follow up for Cohorts 1- 3.

